7.1.1. Liver Chemistry Stopping Criteria

The study drug should be interrupted and close hepatic monitoring initiated (see Section 8.2.2) if 1 or more of these conditions occur:

Elevation ^a	Exception ^a
ALT or AST >8x ULN	
ALT or AST >5x ULN for more than 2 weeks	
ALT or AST >3x ULN and either TBL >2x ULN or INR >1.5	For participants with Gilbert's syndrome: If baseline direct bilirubin is >0.5 mg/dL, then doubling of direct bilirubin should be used for drug interruption decisions rather than TBL >2x ULN.
ALT or AST >3x ULN with the appearance of fatigue, nausea, vomiting, right upper quadrant pain or tenderness, fever, and/or rash	
ALP >3x ULN, when the source of increased ALP is the liver	
ALP >2.5x ULN and TBL > 2x ULN	For participants with Gilbert's syndrome: If baseline direct bilirubin is >0.5 mg/dL, then doubling of direct bilirubin should be used for drug interruption decisions rather than TBL >2x ULN.
ALP >2.5x ULN with the appearance of fatigue, nausea, vomiting, right upper quadrant pain or tenderness, fever, and rash	
Source: FDA Guidance for Industry: Drug-Induced Liver Injury: Premarketing Clinical Evaluation, July 2009 and other consensus guidelines, with minor modifications.	

Abbreviations: ALP = alkaline phosphatase; ALT = alanine aminotransferase; AST = aspartate aminotransferase; INR = international normalized ratio; TBL = total bilirubin; ULN = upper limit of normal.

^a All ULN values should be age adjusted (AAULN) for participants <18 years of age.

Resumption of the study intervention can be considered only in consultation with the Lilly-designated medical monitor and only if liver test results return to baseline and if a self-limiting non-drug etiology is identified. Otherwise, study intervention should be discontinued.

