8.2.2. Hepatic Safety

Close hepatic monitoring^a

Laboratory tests (Appendix 6), including alanine aminotransferase (ALT), aspartate aminotransferase (AST), alkaline phosphatase (ALP), total bilirubin (TBL), direct bilirubin, gamma-glutamyl transferase, and creatine kinase, should be repeated within 48 to 72 hours to confirm the abnormality and to determine if it is increasing or decreasing, if 1 or more of these conditions occur:

If a participant with baseline results of...	develops the following elevations:
ALT or AST <1.5x ULN	ALT or AST ≥3x ULN
ALP <1.5x ULN	ALP ≥2x ULN
TBL <1.5x ULN	TBL ≥2x ULN, except for patients with Gilbert’s syndrome
ALT or AST ≥1.5x ULN	ALT or AST ≥2x baseline
ALP ≥1.5x ULN	ALP ≥2x baseline
TBL ≥1.5x ULN	TBL ≥1.5x baseline, except for patients with Gilbert’s syndrome

Abbreviations: ALP = alkaline phosphatase; ALT = alanine aminotransferase; AST = aspartate aminotransferase; TBL = total bilirubin; ULN = upper limit of normal.

^a All ULN values should be age adjusted (AAULN) for participants <18 years of age.

If the abnormality persists or worsens, clinical and laboratory monitoring, and evaluation for possible causes of abnormal liver tests should be initiated by the investigator in consultation with the Lilly-designated medical monitor. At a minimum, this evaluation should include physical examination and a thorough medical history, including symptoms, recent illnesses (for example, heart failure, systemic infection, hypotension, or seizures), recent travel, history of concomitant medications (including over-the-counter), herbal and dietary supplements, and history of alcohol drinking and other substance abuse.

Initially, monitoring of symptoms and hepatic biochemical tests should be done at a frequency of 1 to 3 times weekly, based on the participant’s clinical condition and hepatic biochemical tests. Subsequently, the frequency of monitoring may be lowered to once every 1 to 2 weeks, if the participant’s clinical condition and lab results stabilize. Monitoring of ALT, AST, ALP, and TBL should continue until levels normalize or return to approximate baseline levels. For participants <18 years of age, special care should be taken to minimize the volume of blood taken during hepatic monitoring.

Comprehensive hepatic evaluation^a

A comprehensive evaluation should be performed to search for possible causes of liver injury if one or more of these conditions occur:

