If a participant with baseline results of...	develops the following elevations:
ALT or AST <1.5x ULN	ALT or AST \geq 3x ULN with hepatic signs or symptoms ^b , or ALT or AST \geq 5x ULN
ALP <1.5x ULN	ALP \geq 3x ULN
TBL <1.5x ULN	TBL \geq 2x ULN (except for patients with Gilbert's syndrome)
ALT or AST \geq 1.5x ULN	ALT or AST \geq 2x baseline with hepatic signs or symptoms ^b , or ALT or AST \geq 3x baseline
ALP \geq 1.5x ULN	ALP \geq 2x baseline
TBL \geq 1.5x ULN	TBL \geq 2x baseline (except for patients with Gilbert's syndrome)

Abbreviations: ALP = alkaline phosphatase; ALT = alanine aminotransferase; AST = aspartate aminotransferase; TBL = total bilirubin; ULN = upper limit of normal.

^a All ULN values should be age adjusted (AAULN) for participants <18 years of age.

^b Hepatic signs or symptoms are severe fatigue, nausea, vomiting, right upper quadrant abdominal pain, fever, and rash.

For Adult Participants (\geq 18 years old)

At a minimum, this evaluation should include physical examination and a thorough medical history, as outlined above, as well as tests for prothrombin time-international normalized ratio; tests for viral hepatitis A, B, C, or E; tests for autoimmune hepatitis; and an abdominal imaging study, for example, ultrasound or computed tomography scan.

Based on the patient's history and initial results, further testing should be considered in consultation with the Lilly-designated medical monitor, including tests for hepatitis D virus, cytomegalovirus, Epstein-Barr virus, acetaminophen levels, acetaminophen protein adducts, urine toxicology screen, Wilson's disease, blood alcohol levels, urinary ethyl glucuronide, and blood phosphatidylethanol. Based on the circumstances and the investigator's assessment of the participant's clinical condition, the investigator should consider referring the participant for a hepatologist or gastroenterologist consultation, magnetic resonance cholangiopancreatography, endoscopic retrograde cholangiopancreatography, cardiac echocardiogram, or a liver biopsy.

For Adolescent Participants (<18 years old)

At a minimum, this evaluation should include physical examination and a thorough medical history, as outlined above, as well as tests for prothrombin time-international normalized ratio and direct bilirubin, if total bilirubin was elevated.

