10.2. Appendix 2: Clinical Laboratory Tests

- The tests detailed in the table below will be performed by the central laboratory.
- In circumstances where the sponsor approves local laboratory testing in lieu of central laboratory testing (in the table below), the local laboratory must be qualified in accordance with applicable local regulations.
- Protocol-specific requirements for inclusion or exclusion of participants are detailed in Section 5 of the protocol.
- Additional tests may be performed at any time during the study as determined necessary by the investigator or required by local regulations.
- Investigators must document their review of the laboratory safety results.

Clinical Laboratory Tests	Comments
Hematology	Assayed by Lilly-designated laboratory
Hemoglobin	
Hematocrit	
Erythrocyte count (RBCs)	
Mean cell volume	
Mean cell hemoglobin	
Mean cell hemoglobin concentration	
Absolute neutrophil count (calculation) (definition – include segs and bands or segs, bands and other immature cells)	
Leukocytes (WBCs)	
Differential	
Percent and absolutes count of:	
Neutrophils, segmented	
Neutrophils, bands	
Lymphocytes	
Monocytes	
Eosinophils	
Basophils	
Platelets	
Cell morphology (RBCs and WBCs)	
Clinical Chemistry	Assayed by Lilly-designated laboratory
Sodium	
Potassium	
Chloride	
Bicarbonate	
Total bilirubin	
Direct bilirubin	
ALP	

Clinical Laboratory Tests	Comments
ALT	
AST	
GGT	
BUN	
Creatinine	
CK	
Uric acid	
Total protein	
Albumin	
Calcium	
Phosphorus	
LDH	
Hormones (female)	
Serum pregnancy	Assayed by Lilly-designated laboratory
Urine pregnancy	Assayed and Evaluated locally
HIV and Hepatitis Serology	Assayed by Lilly-designated laboratory
HIV testing	
HCV testing:	
HCV antibody	
HCV RNA	
HBV testing:	
HBV DNA	Performed only for participants who test positive for HBcAb
HBcAb	
HBsAg	
HBsAb	
Exploratory Biomarkers	Assayed by Lilly-designated laboratory Results will not be provided to the investigative sites
CCI	
Immunoglobulins	Assayed by Lilly-designated laboratory Results will not be provided to the investigative sites
IgE (Serum)	
Genetics Sample	Assayed by Lilly-designated laboratory Results will not be provided to the investigative sites
Exploratory Biomarker storage samples	Assayed by Lilly-designated laboratory Results will not be provided to the investigative sites
Serum	

Clinical Laboratory Tests	Comments
Immunogenicity (ADA) samples	Assayed by Lilly-designated laboratory Results will not be provided to the investigative sites

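### An INR-based liver interruption criterion has no expressly required INR test at ALT/AST >3x to <5x ULN without symptoms, and two symptom rows of the same table use different conjunctions

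*Protocol*

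**What the plan says.** Protocol Section 7.1.1 lists the conditions under which study drug is interrupted and close hepatic monitoring under Section 8.2.2 begins. One row is "ALT or AST >3x ULN and either TBL >2x ULN or INR >1.5". Another is "ALP >2.5x ULN with the appearance of fatigue, nausea, vomiting, right upper quadrant pain or tenderness, fever, and rash". The corresponding ALT/AST symptom row gives the same symptoms but joins the last one with and/or.

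Resumption needs consultation with the medical monitor and is possible "only if liver test results return to baseline and if a self-limiting non-drug etiology is identified". Failing that, the drug is discontinued.

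Four places deal with which liver tests are done:

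- Appendix 2 opens with "The tests detailed in the table below will be performed by the central laboratory". Its hematology and chemistry lists contain no INR and no coagulation panel.
- The Section 8.2.2 repeat-test sentence begins "Laboratory tests (Appendix 6), including alanine aminotransferase (ALT), aspartate aminotransferase (AST), alkaline phosphatase (ALP), total bilirubin (TBL), direct bilirubin" and ends "direct bilirubin, gamma-glutamyl transferase, and creatine kinase, should be repeated within 48 to 72 hours to confirm the abnormality".
- The Section 8.2.2 comprehensive evaluation requires, for adults, examination and history "as well as tests for prothrombin time-international normalized ratio; tests for viral hepatitis A, B, C, or E", among other tests. It names PT-INR for adolescents too.
- Appendix 6 lists PT-INR in a hepatic coagulation panel at the central laboratory, and refers the reader to Section 8.2.2 for the choice of tests.

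**The concern.** A rule that interrupts dosing works reliably only if the measurement it depends on is taken when the rule could apply. Here the first documents a site would follow after a raised ALT or AST do not name INR. A site that orders exactly what is named would not learn whether the INR arm is met until the participant also reaches a threshold for the comprehensive evaluation.

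The conjunction in the ALP row raises a different problem. Two sites with the same patient could reach opposite decisions on interruption, each with a literal or sensible reading of the text.

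What is at stake is consistent application of a safety rule. The trial includes adolescents and has no data monitoring committee. After baseline, the Schedule of Activities plans chemistry only at Weeks 16 and 24, early discontinuation and the follow-up visit, so the repeat draw carries much of the information once an elevation has been seen.

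**Working it through.** The plan states no figure on this point, so there is nothing to reproduce. The check sets the sections side by side and works through the thresholds. It takes a baseline below 1.5x ULN for ALT, AST, ALP and TBL and no Gilbert's syndrome, unless stated.

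**Step 1. Where INR is used and where it is required.**

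| Place in the protocol | Liver tests named | INR |
|---|---|---|
| 7.1.1 | ALT, AST, TBL, INR, ALP | Used as a criterion |
| Appendix 2 | Hematology and chemistry lists | Absent |
| 8.2.2, repeat at 48 to 72 hours | ALT, AST, ALP, TBL, direct bilirubin, GGT, CK (open list, citing Appendix 6) | Not named |
| 8.2.2, continued monitoring | ALT, AST, ALP, TBL | Not named |
| 8.2.2, comprehensive evaluation | PT-INR and others | Required |
| Appendix 6 | Full hepatic list | Listed; selection referred to 8.2.2 |

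**Step 2. The band without a required test.** The comprehensive evaluation starts at ALT/AST ≥5x ULN, at ≥3x with symptoms, at TBL ≥2x, or at ALP ≥3x. None of these is met when ALT/AST is >3x to <5x without symptoms, TBL is <2x and ALP is <3x.

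The other rows of 7.1.1 do not apply in that band either:

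- ALT/AST >8x, or >5x for more than 2 weeks: not met, because ALT/AST is <5x.
- ALT/AST >3x with TBL >2x: not met, because TBL is <2x.
- ALT/AST >3x with symptoms: not met.
- ALP >3x; ALP >2.5x with TBL >2x; ALP >2.5x with symptoms: not met.

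So INR >1.5 is the only thing that could interrupt dosing there, and no sentence expressly requires INR to be measured. From 5x upward the comprehensive evaluation supplies it.

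**Step 3. Raised baseline.** If ALT is 2x ULN at baseline, the symptom-free comprehensive trigger is 3 × 2 = 6x ULN, so the band widens to >3x to <6x. The repeat-test trigger becomes 2 × 2 = 4x ULN, so an ALT of 3.1x with INR >1.5 meets 7.1.1 but lies outside the close-monitoring table, although 7.1.1 itself orders close monitoring.

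**Step 4. The symptom rows.** The ALP row lists six items, counting right upper quadrant pain or tenderness as one. Read as any of them, one of six is enough. Read literally, all six are needed. ALP >3x of liver origin and ALP >2.5x with TBL >2x interrupt in any case. The reading therefore decides the outcome mainly at ALP >2.5x to 3x with TBL not above 2x and some, but not all, of the symptoms.

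**Step 5. Interruption without the comprehensive evaluation.** At normal baseline these interruption profiles fall below every comprehensive trigger:

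- ALT/AST >3x to <5x with INR >1.5 and no symptoms (the band in Step 2);
- ALT/AST >3x to <5x with a symptom that 7.1.1 accepts but the 8.2.2 footnote does not (non-severe fatigue, or tenderness);
- ALP >2.5x to <3x with symptoms;
- in Gilbert's syndrome, where 7.1.1 substitutes direct bilirubin, ALT/AST >3x to <5x or ALP >2.5x to <3x with doubled direct bilirubin.

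All of them meet the 8.2.2 close-monitoring thresholds, so its first-tier evaluation of causes applies if the abnormality continues or gets worse. The minimum content of that evaluation is an examination and a thorough history.

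**The case against.** **INR is available.** The repeat-test list is open and cites Appendix 6, where PT-INR appears. Appendix 2 lets the investigator add tests at any time, and Appendix 6 allows local testing. A reader might infer that the INR criterion cannot be met in practice. The documents do not support that: a site may order INR in the band, and at ALT/AST ≥5x it must. What remains is that permission is not a requirement. Sections 8.2.2 and Appendix 6 refer to each other, and Appendix 6 also holds hepatitis serology, autoantibodies and a drug screen, so it can hardly be mandatory in full at a repeat draw.

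**A cause is looked for.** A reader might infer from Step 5 that some interruptions lead to no search for a cause although resumption depends on one. Section 8.2.2 contradicts this. Every 7.1.1 criterion starts close monitoring, which includes an evaluation of causes when the abnormality does not settle. What remains is narrower: that evaluation is conditional, and its minimum is lighter than the comprehensive one.

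**No route to unsafe re-exposure.** Someone might also read the gap as allowing dosing to restart without an explanation. It does not, because 7.1.1 defaults to discontinuation when no qualifying cause is found.

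**The conjunction is editorial.** The 8.2.2 footnote on hepatic symptoms also uses a plain and, evidently as a list of possibilities. That makes the all-six reading strained. Adjacent rows of one table still differ, and the table governs interruption.

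**Tiering is a legitimate choice.** Section 8.2.2 asks for small blood volumes in participants under 18, and Section 2.3 names no hepatic risk among the potential risks. Both weigh against treating the matter as urgent and against asking for the full work-up after every interruption.

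**Conclusion.** The point holds in a limited form. At normal baseline, the INR arm of 7.1.1 may go unassessed in participants without symptoms who have ALT/AST >3x to <5x ULN, TBL <2x and ALP <3x. The band is wider when baseline ALT or AST is raised. Decisions would differ only for those in the band whose INR is in fact >1.5. The inconsistent conjunction is a second, separate defect, with effect mainly at ALP >2.5x to 3x ULN. That some interruption criteria do not reach the comprehensive evaluation is a mismatch to tidy up, not a safety failure in itself.

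The documents give no frequency for any of these situations, and the number affected may be small. The efficacy estimates are not at issue. The conclusion rests on reading the Appendix 6 citation as a pointer to available tests, and on taking the closing clause about raised total bilirubin in the adolescent sentence of 8.2.2 to qualify direct bilirubin only. It should be corrected because it concerns a dosing-interruption rule and is cheap to put right.

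**What to change.** Reconcile Sections 7.1.1 and 8.2.2, Appendix 2 and Appendix 6 so that the tests expressly required at the repeat draw cover every analyte that a 7.1.1 criterion uses, and end the circular reference between 8.2.2 and Appendix 6. Reconcile the conjunction in the ALT/AST and ALP symptom rows. In the same edit, state whether the interruption criteria in Step 5 are meant to stop at the first-tier evaluation. Which thresholds, tests and wording are clinically right is for the sponsor's medical team to decide.

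The cost is protocol wording and at most one analyte, already in the Appendix 6 central panel, on a repeat draw that takes place anyway. The SAP's planned hepatic summaries use ALT, AST, TBL and ALP, so they need no change.

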7.1. Discontinuation of Study Intervention

When necessary, a participant may be permanently discontinued from study intervention. If so, the participant will remain in the study to complete procedures for an early discontinuation visit and post-treatment follow-up, if applicable, as shown in the SoA.

A participant should be permanently discontinued from study intervention if

- the participant becomes pregnant during the study
- in the opinion of the investigator, the participant should permanently discontinue the study intervention for safety reasons
- the participant develops a malignancy, except for successfully treated basal or squamous cell skin carcinoma
- the participant tests positive for HBV DNA (see Section 8.2.3)
- the participant tests positive for HCV RNA (Section 8.2.4)
- if the participant experiences a hepatic event or liver test abnormality as specified in the liver chemistry stopping criteria (see Section 7.1.1)
- the participant develops HIV infection
- the participant requires rescue medication treatment for symptoms of AD in the treatment period
- the participant develops any infection that is opportunistic, such as active tuberculosis and other infections whose nature or course may suggest an immuno-compromised status, and
- the participant has an AE or an SAE or a clinically significant change in a laboratory value that, in the opinion of the investigator, merits discontinuation of study intervention and appropriate measures being taken.

Hepatitis

- prior to discontinuation of any immunomodulatory and/or immunosuppressive therapy due to hepatitis, including study intervention, the participant is to be referred to, evaluated, and managed by a specialist physician with expertise in evaluation and management of viral hepatitis.
- the timing of discontinuation from study intervention relative to the initiation of any antiviral treatment for hepatitis is to be based on the recommendation of the consulting specialist physician, in conjunction with the investigator, and aligned with medical guidelines and standard of care.

Hypersensitivity

- if the investigator determines that a systemic hypersensitivity reaction has occurred related to study intervention administration, the participant may be permanently discontinued from the study intervention, and the sponsor's designated medical monitor

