8.2.1. Clinical Safety Laboratory Tests

- See Appendix 2 for the list of clinical laboratory tests to be performed and the SoA for the timing and frequency.
- **Local anesthetics**
 - Use of local anesthetics, for example, Eutectic Mixture of Local Anesthetics (EMLA) cream, consistent with local prescribing information are permitted during the study visit to ease discomfort associated with venipunctures.
- The investigator must review the laboratory results, document this review, and consider whether or not any clinically relevant changes occurring during the study constitute as an AE. The laboratory results must be retained with source documents unless a Source Document Agreement or comparable document cites an electronic location that accommodates the expected retention duration. Clinically significant abnormal laboratory findings are those which are not associated with the underlying disease, unless judged by the investigator to be more severe than expected for the participant's condition.
- All laboratory tests with values considered clinically significantly abnormal during participation in the study or within 28 days after the last dose of study intervention should be repeated until the values return to normal or baseline or are no longer considered clinically significant by the investigator or medical monitor.
 - If such values do not return to normal or baseline within a period of time judged reasonable by the investigator, the etiology should be identified and the sponsor notified.
 - All protocol-required laboratory assessments, as defined in Appendix 2, must be conducted in accordance with the SoA, standard collection requirements, and laboratory manual.
- If laboratory values from non-protocol-specified laboratory assessments performed at an investigator-designated local laboratory require a change in participant management or are considered clinically significant by the investigator, for example, SAE or AE or dose modification, then report the information as an AE.

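### Section 7.1.1: the symptomatic ALP stopping row ends in *and* where its ALT/AST counterpart ends in *and/or*, so read literally it needs all six symptoms

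*Protocol*

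**What the plan says.** Protocol Section 7.1.1 lists liver-test conditions, any one of which means that study drug should be interrupted and close hepatic monitoring started. Two rows combine an enzyme threshold with symptoms:

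- ALT/AST row: "ALT or AST >3x ULN with the appearance of fatigue, nausea, vomiting, right upper quadrant pain or tenderness, fever, and/or rash"
- ALP row: "ALP >2.5x ULN with the appearance of fatigue, nausea, vomiting, right upper quadrant pain or tenderness, fever, and rash"

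Two neighbouring ALP rows need no symptoms. One is "ALP >2.5x ULN and TBL > 2x ULN", with an exception for Gilbert's syndrome based on direct bilirubin. The other is ALP above 3x ULN, but only where the liver is the source of the rise.

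Once a row is met, drug may be resumed only in consultation with the medical monitor and "only if liver test results return to baseline and if a self-limiting non-drug etiology is identified"; otherwise it should be discontinued. Section 7.1 also lists these criteria among the grounds for permanent discontinuation.

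**The concern.** The two symptom lists match word for word except for the last connective. A lone *and* at the end of a list would pass as ordinary drafting. Here the same table uses *and/or* for the same list, so a reader may take the difference as deliberate and require fatigue, nausea, vomiting, right upper quadrant pain or tenderness, fever and rash all at once. That would leave the ALP row with almost no function.

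This is an operative safety rule. Meeting the row directs the site to interrupt drug and brings in the restart conditions. Under the literal reading, a participant with a raised ALP and, say, nausea and right upper quadrant pain would trigger neither.

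**Working it through.** No figure in the plan needs reproducing. The check compares the texts and asks where the two readings give different actions.

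**1. Does other text settle the row?**
- The lead-in to the table (one or more conditions) governs rows. It does not say how many symptoms are needed within a row.
- Section 8.2.2 has a similar list in footnote b: "Hepatic signs or symptoms are severe fatigue, nausea, vomiting, right upper quadrant abdominal pain, fever, and rash". It is plainly a catalogue of qualifying symptoms, but it is attached to the ALT/AST criteria for comprehensive evaluation and is not cited in Section 7.1.1.
- No other text in the protocol or SAP says that one symptom is enough for the ALP row.

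**2. Where do the readings differ?** The cases below are illustrative. They assume that no ALT/AST row is met and that the Gilbert's exception does not apply.

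| ALP (x ULN) | Source | TBL (x ULN) | Listed symptoms present | Any one suffices | All six needed |
|---|---|---|---|---|---|
| 2.5 | any | 1 | any number | no row met | no row met |
| 2.75 | liver | 1 | none | no row met | no row met |
| 2.75 | liver | 1 | 1 to 5 | interrupt | **no row met** |
| 2.75 | liver | 1 | all 6 | interrupt | interrupt |
| 2.75 | liver | 2.1 | any number | interrupt (TBL row) | interrupt (TBL row) |
| 3.1 | liver | 1 | any number | interrupt (ALP >3x row) | interrupt (ALP >3x row) |
| 3.1 | non-hepatic or undetermined | 1 | 1 to 5 | interrupt | **no row met** |

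The readings therefore part for participants with one to five symptoms, ALP above 2.5x ULN, TBL not above 2x ULN and no ALT/AST row met. The upper limit on ALP is 3x ULN if the source is the liver. If the source is non-hepatic or undetermined there is no upper limit, because the ALP >3x row does not apply. For a participant with Gilbert's syndrome and baseline direct bilirubin above 0.5 mg/dL, the bilirubin condition is a doubling of direct bilirubin instead.

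**3. What applies under either reading?**
- Section 8.2.2, baseline ALP below 1.5x ULN: ALP at or above 2x ULN means the liver tests "should be repeated within 48 to 72 hours to confirm the abnormality and to determine if it is increasing or decreasing". An ALP of 2.75x ULN passes that threshold. If the abnormality persists or worsens, monitoring and a search for causes follow in consultation with the medical monitor, initially one to three times a week. Hepatic CRF data are collected if ALP is at or above 2x ULN on two or more consecutive tests.
- Section 8.2.2, baseline ALP at or above 1.5x ULN: the repeat-test trigger is twice baseline, which is at least 2 × 1.5 = 3x ULN. Below 3x ULN this safeguard is absent. Exclusion criteria 17 (known cirrhosis or chronic hepatitis) and 37 (clinically significant screening chemistry) should leave few such participants.
- Section 8.2.1: values considered clinically significantly abnormal "should be repeated until the values return to normal or baseline or are no longer considered clinically significant by the investigator or medical monitor".
- Section 7.1: the investigator can stop drug on safety grounds, or for "a clinically significant change in a laboratory value that, in the opinion of the investigator, merits discontinuation of study intervention".

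**4. What do those provisions not replace?** With baseline ALP below 1.5x ULN, comprehensive hepatic evaluation starts at ALP 3x ULN and has no route combining ALP with symptoms. Between 2.5x and 3x ULN, with bilirubin not raised and no ALT/AST row met, the Section 7.1.1 row is the only explicit rule that links ALP and symptoms to a drug stop.

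**5. How often could it arise?** The Schedule of Activities places on-treatment chemistry at Weeks 16 and 24. Main-study dosing ends at Week 20 (responders) or Week 22 (inadequate responders). Apart from early-discontinuation or unscheduled tests and continued access, Week 16 is the one scheduled post-baseline draw after which an interruption could change dosing. It could affect one later dose (Week 20) or three (Weeks 18, 20 and 22). The documents give no frequency for raised ALP with symptoms, so no participant count can be derived.

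**The case against.** The strongest reply is that nobody would apply the row literally. Section 7.1 itself joins alternative discontinuation grounds with a final *and*, Section 7.2 does the same for withdrawal, and footnote b in Section 8.2.2 ends its symptom list the same way. The correct wording stands in the ALT/AST row of the same table. On this view the point is copy-editing, with the safeguards in Sections 7.1, 8.2.1 and 8.2.2 behind it.

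Much of that stands. The all-six reading is unlikely in practice, and the safeguards are real. What does not follow is that the text is adequate. A stopping rule should say how many symptoms it needs, and the contrast within one table invites the wrong answer.

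Three stronger readings are tempting, and the documents do not support them:
- *That the sponsor meant a stricter symptom rule for ALP.* Nothing in either document gives a reason for one, and the list-style *and* elsewhere points the other way.
- *That a participant in the gap is left unmonitored, or that a mandatory stop is lost.* Section 7.1.1 says that drug should be interrupted, and Section 7.1 uses the same verb for the investigator's grounds. The loss is of a specified trigger in favour of a judgment.
- *That the gap closes at 3x ULN.* It does so only when the liver is the source.

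**Conclusion.** The row is wrong as written, as a matter of wording in a safety rule. Read literally it requires six symptoms where one is very likely intended. The intention is an inference from the parallel row and from drafting habits elsewhere in the protocol; no text states it.

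Severity is minor. The effect is confined to the group identified in the working, and only if a site applies the literal reading. For a participant in that group, the protocol would no longer direct interruption and the restart conditions would not come into force. Monitoring, data collection and discretion to discontinue would remain for those with baseline ALP below 1.5x ULN. Those with a higher baseline would rely more on the investigator. That few participants, if any, would be affected is a judgment from the sparse chemistry schedule and the exclusion criteria, not an estimate from data. No endpoint, estimand or efficacy analysis changes. The SAP's hepatic summaries (Section 5.13.6.1) count laboratory thresholds rather than stopping rows, so their definitions do not change either.

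**What to change.** In the symptomatic ALP >2.5x ULN row of Section 7.1.1, replace the closing *and rash* with *and/or rash*, so that any one listed symptom suffices, as in the ALT/AST row. This changes one connective in one table row and can go into the next protocol amendment or a clarification to sites. It adds no assessments, data or participants, and the SAP needs no change.
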